4 HYPOTHESES AND OBJECTIVES

Hypothesis: The prophylactic administration of an antipsychotic with fewer side effects, such as quetiapine, in patients identified with a validated scale decreases the incidence of delirium during the postoperative period compared to placebo administration.

The main objective of the study is to determine the incidence of postoperative delirium in patients at risk, over 65 years of age, treated early with prophylactic quetiapine compared to those treated with placebo.

The secondary objectives are:

- eassess the safety and tolerability of the medication applied.
- cCompare the efficacy of medication versus placebo in relation to:
 - the length of hospital stay.
 - perceived quality of life at 28±2 days from the start (1st dose) of quetiapine treatment.
 - all-cause mortality at discharge and 28±2 days from initiation (1st dose) of quetiapine therapy.
- In cases where delirium develops, know:
 - Time of appearance.
 - the duration and severity of the same.
 - total treatment with other antipsychotics.

5 CLINICAL TRIAL DESIGN.

5.1 . DESCRIPTION OF VARIABLES

The main variable is the proportion of patients diagnosed with delirium (number of delirium cases/total number of patients) in the first 4 postoperative days. We will use a validated scale based on the DSM-IV definition of delirium, CAM: *Confusion Assessment Method* scale (17,24-27).

The secondary variables are:

- 1. Number of days from the start of treatment to the onset of delirium, if it appears.
- 2. duration of delirium, in days.
- 3. severity of theirium measured with validated scale (DRS-R-98).
- 4. D Total osis (mg) haloperidol or another antipsychotic tocontrol the symptoms of delirium.
- 5. Security Costs:
 - Sedation degree: using RASS scale.
 - QTc prolongation: increase in mseg in the control ECG.
 - presence or absence of extrapyramidal symptoms (tremor, involuntary movements, rigidity).
- 6. Days ofhospital stay of the surgical intervention.
- 7. perceived quality of life (through validated questionnaire SF36 or SF 12) 28±2 days after initiation of treatment.
- 8. mortality from all causes at discharge and 28±2 days after initiation of treatment.

Additional variables that will also be collected:

- Baseline variables: demographic data, comorbidity, ASA classification, preoperative medication (sleep medication, antidepressants, opiates, corticosteroids), vital signs, previous baseline analysis with CRP, previous physical function (independent for daily life activities-Barthel index), previous cognitive function (assessed with MINIMental).
- Intraoperative variables: type of intervention and specialty, type of anaesthesia, intraoperative medication related in previous studies with delirium, duration of anaesthesia (min), anesthetic depth and regional cerebral oxygen saturation whenever possible, blood transfusion, degree of pain (by VAS scale) and postoperative medication related in previous studies with delirium and / or analgesic techniques used in this period.
- Complications not associated with delirium that require medical intervention (from grade II on the Clavien-Dindo scale ANNEX 5). They will be collected at the time of the patient's discharge and 28± 2 days after the start of treatment, in percentage. They must be registered in the corresponding section of the CRD, indicating the start date and severity according to the Clavien-Dindo scale. The list of complications to be collected is detailed in ANNEX 6 of this protocol. Inaddition, all those events that in the opinion of the researcher are relevant to the development of the study and patient safety should be collected.

5.2 STUDY DESIGN AND CONTROL METHOD.

Prospective low-intervention, non-commercial, balanced, randomized, double-blind clinical study (phase III).

5.3 PATIENT ASSIGNMENT AND IDENTIFICATION CODES.

Patientswill be identified with a code that will be generated with protocol code (QUEPRO) + correlative number, according to orrdin inclusion in the study. Example: The first patient included in the trial will receive the identification code QUEPRO-001; the second QUEPRO-002 and so on.

Once the patient accepts participation in the study by signing the informed consent, his participation has been correctly recorded in his medical history and it has been verified that he meets all the inclusion criteria and none of the exclusion criteria, the subject will be assigned an identification code and will be centrally randomized by the sponsor with a 1:1 ratio in one of the two arms of the study, placebo (control group) or quetiapine (experimental group) in a consultation prior to surgery (selection visit), in such a way that proportional groups with equal probability of permanence are generated.

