1.10 CLINICAL TRIAL PHASE Phase III

10.110BJECTIVES

Main: to know the incidence of postoperative delirium in patients at risk, over 65 years of age, treated early with prophylactic quetiapine compared to those treated with placebo.

Side:

- 1. Evaluate the safety and tolerability of the medication applied
- 2. To compare the efficacy of medication versus placebo in relation to:
 - length of hospital stay
 - perceived quality of life
 - all-cause mortality at discharge and 28±2 days from initiation (1st dose) of quetiapine treatment.
- 3 In cases where delirium develops, know:
 - Time of appearance
 - the duration and severity of the same
 - Total dose of treatment with other antipsychotics.

1.12STUDY DESIGN

Prospective low-level non-commercial, balanced, randomized, double-blind clinical trial (phase III) clinical trial.

1.13STUDY DISEASE

Delirium developed during the period after surgery.

Delirium is an acute alteration of consciousness accompanied by inattention, disorganization of thought and alterations of perception that fluctuate in a short period of time (DSM IV). It is one of the most frequent complications of surgery and develops characteristically between 0-96 h after the intervention. It is associated with worse prognosis in the short and long term.

1.14STUDY VARIABLES

- A. The main variable is the proportion of patients diagnosed with delirium (number of delirium cases/total number of patients) in the first 4 postoperative days in both branches.
- B. Secondary variables:
 - 1. number of days from the start of treatment to the onset of delirium, if it appears,
 - 2. duration of delirium, in days,
 - 3. severity of delirium measured with validated scale (DRS-R-98)
 - 4. total dose (mg) haloperidol or another antipsychotic to control symptoms of delirium,
 - 5. Security variables:
 - degree of sedation: by RASS scale,
 - QTc prolongation: increase in mseg on the control ECG.
 - presence or absence of extrapyramidal symptoms (tremor, involuntary movements, stiffness)
 - 6. days of hospital stay since surgery,

- 7. perceived quality of life (through SF36 validated questionnaire) 28±2 days after initiation of treatment,
- 8. All-cause mortality at discharge and 28±2 days after initiation of treatment

1.15STUDY POPULATION AND TOTAL NUMBER OF PATIENTS

Patients older than or equal to 65 years of age who are going to undergo major non-cardiac surgery and who have a score equal to or greater than 5 on the Delphi scale:

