
Given the importance of this condition, its prevalence and its consequences, we think that prophylaxis in the population at risk (patients >65 years postoperative for non-cardiac surgery) during the first 72 hours after surgery with small doses of quetiapine can provide great benefits (decreased incidence, decreased duration and severity delirium) with a low level of risk since it has a favorable safety profile.

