- Basal cognitive function (valued with MINIMental o 6 ICT).
- CAM scale.
- ECG and QTc measurement.
- III. Postoperative visits: A daily personal clinical visit will be made to all randomized patients during the first four days of the postoperative period or during the duration of their admission if it is less than 4 days. In this case, the last visit during admission will be the visit to discharge.

These clinical visits will be listed in corresponding to the postoperative day: visit 1st day post, visit 2nd day post... so on until the 4th postoperative day.

Procedures to be performed:

- CAM scale.
- RASS scale.
- Extrapyramidal symptoms.
- vital signs.
- ECG and QTc measurement (after administration of the 4th dose).
- Complete laboratory tests (at least one during the first four days after surgery).
- VAS scale and analgesia received (opiates).

In addition, during the 1st postoperative visit, the intraoperative variables will be collected:

- Type of surgical intervention and specialty.
- urgent ly programmed.
- anesthetic technique performed.
- Drugs used, doses and routes of administration(benzodiazepines, opiates, glucocorticoids, atropine).
- Measurement of anesthetic depth and/or regional brain oxygen saturation where possible.
- Duration anesthesia .
- EVA upon admission to URPA/Resuscitation.
- Analgesia: IV or by regional techniques(drug used, dose and administration).
- blood transfusion.

If the patient develops delirium, the daily visit will continue until the clinic disappears. In this case, the following will also be collected:

- severity of the picture using DRS scale -R- 98
- Drug used for its treatment, dose and route of administration.

- IV. Discharge visit: when the patient meets criteria and is discharged. The following will be collected:
 - Reason for hospital discharge.
 - CAM.
 - RASS.
 - vital signs.
 - Extrapyramidal symptoms.
 - Hospital evolution including complications that have appeared and that have required medical treatment (≥ grade II Clavien-Dindo scale): blood transfusion, surgical reoperation, pneumonia
 - mortality.
 - complete anal itatic if it has not been collected in the postoperative visits.
 - If you have developed delirium:
 - × duration.
 - × Severity.
 - × Dosage and route of administration of the drug used for its treatment.

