8 N-ASSESSMENTOF EFFECTIVENESS

8.1 EFFICACY VARIABLES.

The efficacy of the treatment is given by the main variable: incidence of delirium during the postoperative period in the first 4 days in both intervention groups.

The secondary variables will be collected: number of days free of delirium, duration and severity of delirium if it finally develops; hospital stay, adverse effects, mortality at discharge and 28 ± 2 days, perceived quality of life at 28 ± 2 days.

8.2 EVALUATION METHODS.

To obtain the main variable we will use the CAM scale (Confusion Assessment Method) as a method of diagnosis of the appearance of delirium. It is a scale based on the DSM IV definition of delirium (29) and with demonstrated internal and external validity for surgical patients (17,24-27). It consists of an interview of the clinician consisting of six items: two addressed to the closest caregiver (family member or nursing technician) with which information is obtained on the beginning of the picture and the presence of fluctuations. The remaining four items are to ask the patient, to determine their cognitive impairment that evaluates attention, thinking and consciousness. In the second part of the instrument, the clinician answers a questionnaire of 4 questions (yes / no), based on the evaluation made. The diagnosis of delirium is established around the presence of its two fundamental criteria (abrupt onset with fluctuations of symptoms and loss of attention) and one of the two secondary criteria (disorganized thinking and altered level of consciousness). We will use the same scale to rule out the presence of delirium in the initial assessment of the patient and to determine the duration of the picture during the follow-up period. The assessment of the response will be carried out daily in both study groups, during the first 4 days of admission or until the patient's discharge.

We will use the RASS scale (Richmond Agitation sedation scale) to assess the degree of sedation or agitation presented by the patient. It is a 10-point scale, very intuitive in its description since the positive values indicate agitation and the negative values are used to quantify sedation, in such a way that level 0 corresponds to a calm and awake patient, level 4

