to the situation of maximum agitation and level -5 to the highest depression of the level of consciousness. It also has a good correlation with the appearance of delirium when the presence or absence of attention is detected (30). It will be administered prior to CAM during the follow-up period, if -4/-5 values are obtained, it will be repeated again after two hours until it decreases to -3 values onwards. In case of development of delirium, daily follow-up (through CAM and RASS scales) will be carried out until resolution of the patient's condition or discharge and the drugs used for symptom control and the necessary doses will be recorded in the CRD.

The severity of delirium developed will be determined by the DRS-R-98 scale (31,32). Itis a scale of 16 items scored by the clinician with two sections (severity and diagnosis) and a score sheet. The 13 items in the severity section can be scored separately from the 3 items in the diagnostic section. The severity section functions as a standalone scale for repeated measurements during an episode of delirium. All items are accompanied by descriptions that serve as a guide for scoring along a continuum that moves between normality and severe involvement, scoring between 0 and 3. All available sources of information can be used for patient assessment: family, visitors, hospital staff, even the roommate can contribute more information. Some items are scored based on test and medical history, while others incorporate standardized questions (e.g., language and cognitive items). The items assessed are: circadian rhythm alteration, alterations in perception and hallucinations, delusions, affective lability, language alterations, alterations in the course of thought, agitation or motor slowdown, orientation, attention, short and long-term memory, visuospatial capacity. Only the severity section of the scale will be administered once a day for as long as you develop delirium.

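### Onset, duration, severity and antipsychotic dose are defined only in patients who develop delirium, and the general test rule in section 10 would compare the arms within that outcome-selected group

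*Combined protocol and SAP*

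**What the plan says.** Sections 1.11 and 4 sort the secondary objectives by wording. For stay, quality of life and mortality the aim is "To compare the efficacy of medication versus placebo in relation to". For time of appearance, duration, severity and other antipsychotic treatment it is "In cases where delirium develops, know". Section 8.1 repeats the condition for two of these: "number of days free of delirium, duration and severity of delirium if it finally develops". The delirium-free days named there are not defined; the nearest item in the variable lists (1.14, 5.1) is days from start of treatment to onset, if delirium appears.

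Collection follows the same condition:
- DRS-R-98 (8.2): "Only the severity section of the scale will be administered once a day for as long as you develop delirium".
- Drug, dose and route are collected under the trigger in 7.2, "If the patient develops delirium, the daily visit will continue until the clinic disappears", and 7.3 also ties their recording to delirium developing.
- The dose variable in 1.14 is one milligram total: "total dose (mg) haloperidol or another antipsychotic to control symptoms of delirium".

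Section 3 expects "decreased incidence, decreased duration and severity delirium". Section 10 says that all efficacy and safety variables are analysed for both arms, compares continuous variables with t or Mann-Whitney tests, and makes all analyses two-sided hypothesis tests at 5%. It names per-protocol and intention-to-treat analysis, and multivariate and survival models to check for confounding. No section gives a value, or any other rule, for patients without delirium.

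**The concern.** Whether a patient is a case is the primary outcome, which quetiapine is meant to change. If it works, the cases left on quetiapine are those it failed to prevent, while the placebo cases include patients whom it would have spared. The two groups can then differ in expected duration, severity or drug requirement even if quetiapine does nothing to an episode once it occurs.

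Nothing in section 10 repairs this. Intention to treat supplies no value for non-cases. Adjustment for measured covariates cannot be relied on to remove selection on the severity that a patient would have had. At stake is a secondary result reported as benefit or harm of quetiapine when it reflects only which cases were prevented.

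**Working it through.** **Inputs.** Section 6.3: control incidence 20–25%, absolute reduction 12 points, 175 per arm, 80% power, 5% losses. Section 10: two-sided 5%.

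**The plan's own figure.** With pooled variance, n per arm = [1.96·√(2·p̄·(1−p̄)) + 0.8416·√(p0(1−p0)+p1(1−p1))]² / (p0−p1)². At 25% vs 13%, p̄ = 0.19 and n = (1.087 + 0.461)²/0.0144, which rounds up to 167. Then 167/0.95 rounds up to 176, a total of 352 against the stated 350. The midpoint, 22.5% vs 10.5%, with continuity correction gives exactly 350. At 20% vs 8% the total is 276, or 310 with correction. So 350 fits the upper part of the plan's range; the lower end is kept below because section 6.3 includes it.

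**Size of the case-only groups.**
- 25% vs 13%: 175 × 0.25 = 43.75 and 175 × 0.13 = 22.75; 66.5/350 = 19%.
- 20% vs 8%: 175 × 0.20 = 35 and 175 × 0.08 = 14; 49/350 = 14%.
- After 5% losses (× 0.95): about 42 vs 22, or 33 vs 13.

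**Precision.** The 95% CI half-width in SD units is t(0.975)·√(1/n0 + 1/n1). This is 2.00 × √(1/43.75 + 1/22.75) = 0.52, or 2.01 × √(1/35 + 1/14) = 0.64.

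**Selection effect (illustration).** Let would-be severity S be Normal(0,1) among patients who would be cases on placebo. On quetiapine such a patient remains a case with probability 1/(1+exp(−(a+bS))). The constant a is set so that the average equals p1/p0 (0.13/0.25 = 0.52; 0.08/0.20 = 0.40). The drug does not alter S in cases that occur. A t test is run among cases with 175 per arm. The link b, in log-odds per SD, is an assumption. Significant results in one direction, against 2.5% nominal:

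| Effect | b = 0 | 0.25 | 0.5 | 1 |
|---|---|---|---|---|
| Full: 25% vs 13%, 20% vs 8% | 2–3% | about 7% | 13–14% | 33–35% |
| Half: 25% vs 19%, 20% vs 14% | 2–3% | about 4% | 7–8% | 14–16% |
| 25% vs 22% | 2–3% | about 3% | 4–5% | 7% |

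Positive b gives false worsening. Negative b of the same size gives false improvement at essentially the same rates.

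**Duration.** Assume geometric episodes with mean 2 days. At 25% vs 13%, the case-only Mann-Whitney test gives false worsening in 11% and 27% of trials at b = 0.5 and 1, and false improvement in 11% and 29% at −0.5 and −1. In the same trials, delirium days in all randomised patients (0 for non-cases) differ by −0.30 to −0.18 days per patient. They favour quetiapine in 91% to 35% of trials, and placebo in at most 0.2%.

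**The case against.** The strongest reply is that no case-only test is planned. The hypothesis in section 4 concerns incidence alone. The objectives reserve comparison for stay, quality of life and mortality. Section 8.1 says that efficacy is given by the main variable and that the secondary ones will be collected. It does not list antipsychotic dose, and its list includes adverse effects, so being listed there does not make an item an efficacy test. Analysing a variable for both arms could mean a summary per arm, and the expected reductions in section 3 are background.

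This stands far enough that a reader who infers a specified case-only test goes beyond the text. It does not remove the problem. The two-sided test rule in section 10 covers all analyses without exception, and section 3 states an expected gain in duration and severity. An analyst following section 10 would run the test.

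It is also fair that the larger false-result rates need both the full 12-point effect and a substantial link, for which the documents give no basis. A reader might infer that a third of such tests would mislead, or that the error would make quetiapine look harmful. Neither is supported. Section 3 does report an olanzapine trial with lower risk (RR 0.36) but longer and more severe episodes. That shows such a result can arise and is ambiguous; it does not show that selection caused it.

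Finally, all-randomised delirium days partly repeat the incidence result. That is correct, and is why the case-only estimates should be kept.

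**Conclusion.** The point holds for secondary outcomes. The plan conditions four of them on the primary outcome, gives no value for non-cases, and has a general test rule that would compare the arms within 14–19% of those randomised. Selection could produce false benefit or false harm. The rate in one direction runs from nominal with no link to 13–35% at the full planned effect with links of 0.5 to 1 log-odds per SD. It is about 7% at a link of 0.25, and lower at smaller effects. These rates rest on the assumed link and a Normal severity scale; neither size nor direction can be learned from the documents. Time to onset has the same conditioning but was not simulated.

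A reader might infer that the trial's main conclusion is weakened. It is not: the primary proportion uses all patients, and neither its analysis nor the 350 is touched. The change should be made, and fixed before unblinding so that the rule cannot be chosen by result.

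**What to change.** In sections 5.1, 8.1 and 10:

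1. State that case-only time to onset, duration, DRS-R-98 severity and antipsychotic dose are reported by arm as estimates with 95% confidence intervals. Label them descriptive, with no hypothesis test and no claim of benefit or harm.
2. Make the between-arm comparison of delirium burden in all randomised patients: days with delirium from episodes starting in the first 4 postoperative days, counted to resolution or discharge, with 0 by definition for patients without delirium. The data are already planned (8.2): "In case of development of delirium, daily follow-up (through CAM and RASS scales) will be carried out until resolution" or discharge. Add a short rule for death, discharge before day 4 (7.2) and withdrawal, after which follow-up stops (6.5). Stopping the count at day 4 would discard about 9–40% of delirium days under assumed mean durations of 2 to 3 days and onset on days 1–2 or 1–4.
3. Compare any antipsychotic use for delirium (yes/no) in all randomised patients, with no use by definition for non-cases. Report dose separately by drug, since milligrams of different drugs do not add.

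The cost is a few sentences and a short missing-data rule, with no new visit, scale or patient. The all-randomised measures mix incidence with duration, so the case-only estimates stay beside them.

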5.4 DESCRIPTION OF TRIAL TREATMENTS

Quetiapine is a drug belonging to the group of atypical antipsychotics with extensive experience of use in humans. Generic presentation is currently available. The smallest dose marketed in Spain is 25 mg in the form of film-coated tablets whose composition is: 25 mg quetiapine as quetiapine fumarate and 18.5 mg lactose as excipient. It is administered orally or enterally by crushing it previously.

For the realization of this clinical trial we will use doses of 25 mg every 12 hours for 3 days, so the total dose used per patient will be 150 mg of quetiapine.

Adverse reactions reported for quetiapine:

According to the Summary of Product Characteristics published by Normon S.A. revised in July 2018, themost frequently reported adverse drug reactions (ADRs) with quetiapine (\geq 10%) are drowsiness, dizziness, dry mouth, headache, withdrawal symptoms (discontinuation), elevated serum triglyceride levels, elevated total cholesterol (predominantly LDL cholesterol), decreased HDL cholesterol, weight gain, decreased hemoglobin, and extrapyramidal symptoms. ANNEX 7 details the ADRs associated with quetiapine treatment and their corresponding indications. The frequencies of adverse events are classified as Very common (\geq 1/10), common (\geq 1/100, <1/10), uncommon (\geq 1/1,000, <1/100), rare (\geq 1/10,000, <1/1,000), very rare (<1/10,000) and not known (cannot be estimated from the available data).

The placebo is prepared in hard gelatin capsules in such a way that the capsules are identical to those containing active ingredient so that it is impossible to differentiate. Placebo consists of microcrystalline cellulose and magnesium stearate.

5.5 MASKING TECHNIQUES AND OPENING OF MASKING CODES.

This work is designed as double-blind, so that neither the patient nor the researcher know the branch of the study assigned to each patient.

At the pre-intervention screening visit, the patient is assigned a code (identification code) and randomization is performed, all centrally. Upon arrival at Resuscitation / Post-anesthetic Recovery Unit after the intervention, the pharmacy is requested to prepare the medication corresponding to that code. The preparation will be marked as quetiapine/placebo, which will be what the doctor in charge of the patient's care writes in the treatment orders, thus respecting the masking. The active drug/placebo will be coated with an identical gelatin capsule so that neither the patient nor the patient's attending physician can identify which of the products they are administering.

The cecum will be maintained until after the data analysis is performed. The blind for a specific patient should only be broken when information about the patient's treatment protocol is considered necessary and essential. The unmasking procedure shall be requested only by the principal investigator and/or his/her representative and with the consent of the sponsor. If an urgent intervention is necessary so as not to compromise the safety and/or life of the patient, the blind can break without the express authorization of the sponsor, but must be notified within a maximum period of 24 hours.

5.6 IDENTIFICATION OF THE DATA TO BE RECORDED.

The patient data necessary to obtain the primary, secondary and complementary variables will be collected in the paper data collection notebooks (CRD) and must be documented in accordance with the guide of Good Clinical Practice, confidentiality and data protection law. The data included in the CRD, which are derived from source documents, must be consistent with those documents or otherwise justify the discrepancies.

Retention of documentation: the investigator will keep the original clinical documents of each patient in the study, which consist of all medical and demographic information including

laboratory data, electrocardiograms, etc., and a copy of the signed informed consent form, for as long as established by the legislation in force after the end or suspension of the study. Uponsigning the protocol, the researcher agrees to follow the procedures for preserving documents.

